5.2.5 Timing of Dose Administration

Each subject may undergo up to 35 cycles (approximately 2 years) of MK-1454 treatment in both the monotherapy arm (Arm 1) and the combination therapy arms (Arm 2 and Arm 3), as well as the Expansion Cohorts (Cohort A to C).

After C1D1, trial treatment may be administered up to 3 days before, or up to 3 days after the scheduled treatment day within each cycle. Dosing interruptions are permitted in the case of medical/surgical events or logistical reasons that are not related to study therapy (eg, elective surgery, unrelated medical events, patient vacation, and/or holidays). Subjects should be placed back on study therapy within 3 weeks of the scheduled interruption, unless otherwise discussed with the Sponsor Medical Monitor or designee. The reason for interruption should be documented in the subject's study record.

5.2.5.1 Timing of MK-1454 Dose Administration in Part I - Dose Escalation and Confirmation

MK-1454 will be administered on Day 1, Day 8, and Day 15 in each 21-day cycle for Cycles 1, 2, and 3 for Arms 1 and 2. Beginning with Cycle 4, MK-1454 will be administered on Day 1 of each 21-day cycle.

For Arm 3, MK-1454 will be administered IT to visceral lesions at escalating frequencies	es. Ir
the ATD phase, MK-1454 will be administered CCI	In the
mTPI phase, frequency of administration will begin with Escalation of frequency	/ may
proceed first to a CCI	on
Day 1 of Cycle 3 and beyond. Escalation of frequency may then proceed to	
After Cy	cle 3
frequency of visceral IT administration may be modified by the investigator based on cli	inica
assessment of the investigator and discussion with the Sponsor.	

In Arm 2 and Arm 3 of the trial, MK-1454 will be administered within 0.5 to 4 hours following completion of pembrolizumab infusion.

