5.2.5.3 Timing of Pembrolizumab Administration

Pembrolizumab 200 mg will be administered as an IV infusion on Day 1 of each 21-day cycle, in all combination treatment arms in Part I and Part II.

Protocol/Amendment No.: 001-08

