Plasma MK-1454 PK b,c	X			X						X°	Collect predose samples 1-8 h before MK-1454 administration on C1D1 and C2D1. Collect postdose samples on C1D1 and C2D1 at the following time points: end of IT injection (up to +15 min), 0.5 h (±15 min), 1 h (±15 min), 1.5 h (±15 min), 4 h (±15 min), and 6 h (±15 min). Additional postdose samples will be collected at 12 h (±2 h) and 24 h (±4 h) following MK-1454 IT administration on C1D1 only. If applicable, collect on Day 1 of the first cycle that the subject has undergone intrasubject dose escalation of MK-1454. Collect samples at the same time as for cytokines and CRP, and for pembrolizumab PK, when feasible.
Serum for Pembrolizumab PK	X			X						X	Pembrolizumab PK and ADA are for pembrolizumab-
Serum for ADA	X			X						X	treated subjects only. Collect samples predose 0 to 4 h before pembrolizumab IV infusion on C1D1, C2D1, C4D1, and on Day 1 of every 4 cycles thereafter (ie, C8, C12, etc.). Collect pembrolizumab and MK-1454 PK samples together, when feasible.
Blood for Plasma Biomarker Analysis				X						X	Collect prior to MK-1454 administration (Arm 1) and prior to pembrolizumab administration (Arm 2) on C2D1 and
Blood for Serum Biomarker Analysis				X						X	C5D1.
Blood for RNA Analysis	X									с	Collect predose 0-4 h before MK-1454 administration on C1D1. Collect postdose 6 h (±15 min) after MK-1454 administration on C1D1.
Blood for Genetic Analysis d	X										Collect prior to treatment.

Protocol/Amendment No.: 001-08

					Monot		Cycle =				
Trial Period	MK	-1454 a	ınd Per	nbroliz 	umab (Combin	ation Th	ierapy	Cycle =	Cycle 4	
Cycle		Cycle 1	ycle 1 Cycle 2		(Cycle 3			Notes		
Scheduling Day	1	8	15	1	8	15	1	8	15	1	
Scheduled Window	±3	±3	±3	±3	±3	±3	±3	±3	±3	±3	
Tumor Tissue Biopsy ^e									Х	X	For the tumor lesion that is treated with IT administration of MK-1454, collect postdose tumor biopsy on the same day as treatment, 5 h (\pm 2 h) following IT administration of MK-1454 on C3D15, and optionally on C6D1 at 5 h (\pm 2 h) following IT administration of MK-1454. Biopsy of a distant, discrete, noninjected site is preferred on the same day as the IT administration of MK-1454, but may be performed up to 3 days after treatment of the injected lesion. The C6D1 biopsy time point is encouraged, but optional.

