CBC with Differential	X	X	X	X	X	X	X	X	
PT/INR and PTT or aPTT	X			X			X	X	D ' 1 '4' 701 (CIDI D 4 14 1 4 1'C
Chemistry Panel	X	X	X	X	X	X	X	X	Required within 72 h of C1D1. Does not need to be repeated if screening labs were done within 72 hours of C1D1. May be performed
LDH, GGT	X			X			X	X	up to 72 h prior to dosing for subsequent cycles when scheduled.
Urinalysis	X			X			X	X	up to 72 ii prior to dosnig for subsequent cycles when scheduled.
Lipase and Amylase	X			X			X	X	
Pregnancy Test for WOCBP – Urine or Serum hCG	X								Required within 24 h prior to first dose of study medication. Does not need to be repeated if screening test was done within 24 hours of C1D1. If a urine pregnancy test cannot be confirmed as negative, a serum pregnancy test is required. Pregnancy testing must be done as required by local regulation. Where local regulations require monthly pregnancy testing per CTFG guidelines, see Appendix 12.5.

Protocol/Amendment No.: 001-08

Trial Period				nothera	ру Сус			Q3W py Cycle =	
								Cycle 4 and	
Cycle	Cycle 1			Cycle 2			Cycle 3	Beyond	Notes
Scheduling Day	1	8	15	1	8	15	1	1	
Scheduled Window	±3	±3	±3	±3	±3	±3	±3	±3	
Thyroid Function (T4, FT4, T3, FT3, TSH)	X						X	X	To be performed within 72 hours prior to Day 1 of C1, C3, C5, C7, C9, C11, and at every other subsequent treatment cycle. Does not need to be repeated if screening labs were done within 72 hours of C1D1.
Pharmacokinetics (PK)/ Pharmacodynamics/ Future Biomedical Research/Biomarkers									See Procedures Manual for Collection and Management of Samples.
Serum for Cytokine Panel and CRP for MK-1454 Pharmacodynamics ^b	X			X				Xp	Cytokine and CRP samples should be obtained predose on C1D1 and C2D1 either both in the morning (8 AM to 12 PM) or both in the afternoon (1 PM to 5 PM). Postdose serum samples for cytokine panels and CRP will be collected on C1D1, C2D1, and C5D1. Postdose samples will be collected at 4 h (±15 min) and 6 h (±15 min) after MK-1454 administration. On C1D1, an additional serum sample will be collected at 12 h (± 2 h) and 24 h (± 4 h) following MK-1454 administration. Collect samples at the same time as for MK-1454 PK when feasible.

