Plasma MK-1454 PK	X			X				X^{b}	Collect predose samples 1-8 h before MK-1454 administration on C1D1 and C2D1. Collect postdose samples on C1D1 and C2D1 at the following time points: end of IT injection (up to +15 min), 0.5 h (±15 min), 1.0 h (±15 min), 1.5 h (±15 min), 4 h (±15 min), and 6 h (±15 min). Additional postdose samples will be collected at 12 h (±4 h) and 24 h (±4 h) following MK-1454 IT administration on C1D1 only. Collect samples at the same time as for cytokines and CRP, and for pembrolizumab PK, when feasible.
Serum for Pembrolizumab PK	X			X				X	Collect samples predose 0 to 4 h before pembrolizumab IV infusion
Serum for ADA	X			X				X	on C1D1, C2D1, C4D1, and on Day 1 of every 4 cycles thereafter (ie, C8, C12, etc.). Collect with plasma samples for MK-1454 PK when feasible.
Blood for Plasma Biomarker Analysis				X				X	Collect prior to MK-1454 administration (Arm 1) and prior to pembrolizumab administration (Arm 2 and Arm 3) on C2D1 and
Blood for Serum Biomarker Analysis				X				X	C5D1.

087V73

Protocol/Amendment No.: 001-08

Trial Period	Treatment Phase MK-1454 Monotherapy Cycle = Classical then Q3W MK-1454 and Pembrolizumab Combination Therapy Cycle = 21 Days								
Cycle	Cycle 1		Cycle 2			Cycle 3	Cycle 4 and Beyond	Notes	
Scheduling Day	1	8	15	1	8	15	1	1	
Scheduled Window	±3	±3	±3	±3	±3	±3	±3	±3	
Blood for RNA Analysis	X								Collect predose 0-4 h before MK-1454 administration on C1D1 Collect postdose 6 h (±15 min) after MK-1454 administration on C1D1.
Blood for Genetic Analysis ^c	X								Collect prior to treatment.
Tumor Tissue Biopsy ^d							X	X	For the tumor lesion that is treated with IT administration of MK-1454, collect predose tumor biopsy on the same day as treatment prior to IT administration of MK-1454 on C3D1, or up to 3 days prior to treatment on C3D1, and optionally on C6D1 prior to IT administration of MK-1454, or up to 3 days prior to treatment on C6D1. If available, biopsy of a distant, discrete, noninjected site is preferred on the same day as the IT administration of MK-1454 but may be performed up to 3 days after treatment of the injected lesion. The C6D1 biopsy time point is encouraged, but optional.

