Trial Period	Screening			MK-1	454 C Pem	ycle =	CCI	ent Ph th Cyclo		W; or Q3V Days		
Cycle	Screening		Cycle	1	(Cycle 2	2		Cycle 4 and Beyond		and	Notes
Scheduling Day	-28 to -1	1	8	15	1	8	15	1	8	15	1	
Scheduled Window		±3	±3	±3	±3	±3	±3	±3	±3	±3	±3	
Serum for Pembrolizumab PK		X			X						X	Collect samples predose 0 to 4 h before pembrolizumab IV infusion on C1D1, C2D1, C4D1, and on Day 1 of every 4
Serum for ADA		X			X						X	cycles thereafter (ie, C8, C12, etc.). Collect pembrolizumab and MK-1454 PK samples together, when feasible.
Blood for Plasma Biomarker Analysis					X						X	Collect prior to MK-1454 administration (Arm 1) and prior to pembrolizumab administration (Arm 2) on C2D1 and C5D1.
Blood for Serum Biomarker Analysis					X						X	
Blood for RNA Analysis		X										Collect predose 0-4 h before MK-1454 administration on C1D1 Collect postdose 6 h (±15 min) after MK-1454 administration on C1D1.
Blood for Genetic Analysis ^c		X										Collect prior to treatment.
Tumor Tissue Biopsy ^d	Х				X			X				For the tumor lesion that is treated with IT administration of MK-1454, collect predose tumor biopsy on the same day as treatment prior to IT administration of MK-1454, or up to 5 days prior to treatment on C2D1 and on C3D1 (optional). If available, biopsy of a distant, discrete, noninjected site may be performed up to 5 days before treatment of the injected lesion.

AE = adverse event; aPTT = activated partial thromboplastin time; CBC = complete blood count; CRP = C-reactive protein; CT = computed tomography; CTCL = cutaneous Tcell lymphoma; ECOG = Eastern Cooperative Oncology Group; EOT = end of treatment; FBR = future biomedical research; (F)T3 = (free) triiodothyronine; (F)T4 = (free) thyroxine; GGT = gamma glutamyl transferase; hCG = human chorionic gonadotropin; HCV = hepatitis C virus; HIV = human immunodeficiency virus; HNSCC = Head and Neck Squamous Cell Carcinoma; HPV = human papillomavirus; INR = international normalized ratio; irRECIST = immune-related RECIST; ISCL = International Society for Cutaneous Lymphomas; IT = intratumoral; LDH = lactate dehydrogenase; MRI = magnetic resonance imaging; NASBA = nucleic acid sequence-based amplification; PET = positron emission tomography; PK = pharmacokinetics; PT = prothrombin time; PTT = partial thromboplastin time; RECIST v1.1 = Response Evaluation Criteria In Solid Tumors, version 1.1; RNA = ribonucleic acid; TSH = thyroid-stimulating hormone; WOCBP = women of childbearing potential.

087V73

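### In Arm 3 the injected lesion is biopsied before the Cycle 3 Day 1 dose, but the paired noninjected lesion may be biopsied up to 3 days after it, so some pairs can straddle a dose

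*Combined protocol and SAP*

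**What the plan says.** Section 6.1.3 gives the two lesions of an Arm 3 pair different windows. For the injected lesion, sites are to "collect predose tumor biopsy on the same day as treatment prior to IT administration of MK-1454 on C3D1, or up to 3 days prior". For the distant lesion, biopsy of a "noninjected site is preferred on the same day as the IT administration of MK-1454 but may be performed up to 3 days after treatment". The optional Cycle 6 Day 1 pair is covered by the same note. Section 2.1.1 places the Arm 3 biopsy on Cycle 3 Day 1 without saying before or after dosing.

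Both drugs are scheduled that day. Section 5.2.5.3 states: "Pembrolizumab 200 mg will be administered as an IV infusion on Day 1 of each 21-day cycle". Section 5.2.5.1 has Arm 3 MK-1454 given on "Day 1 of Cycle 3 and beyond" (the frequencies are partly redacted), 0.5 to 4 hours after the infusion ends.

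The other schedules differ. In Section 6.1.2 (Arms 1 and 2) the injected lesion is sampled 5 h ± 2 h after the injection, and the "noninjected site is preferred on the same day as the IT administration of MK-1454, but may be performed up to 3 days after treatment". In Section 6.2.1 (Part II) the injected lesion is sampled predose, up to 5 days ahead, and the "noninjected site may be performed up to 5 days before treatment of the injected" lesion.

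The Arm 3 table also has a blood-sampling mismatch. Its note reads "Cytokine and CRP samples should be obtained predose on C1D1 and C2D1 either both in the morning" or both in the afternoon, yet postdose samples are listed for Cycles 1, 2 and 5. Sections 6.1.2 and 6.2.1 list a predose sample at Cycle 5 Day 1 as well.

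**The concern.** The Arm 3 noninjected-lesion text is almost the same as that for Arms 1 and 2, where it sits beside a postdose injected-lesion biopsy. In Arm 3 the injected-lesion biopsy is predose, and no reason is given for leaving the noninjected window running forward from the dose. It reads like a carry-over.

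When the forward window is used, the injected lesion reflects the interval since the previous injection and the noninjected lesion reflects the hours or days after a new one. Section 4.2.3.4 describes type I interferons, proinflammatory cytokines and chemotactic factors as the immediate mediators of the drug class, so time since dose could plausibly affect what the tissue shows. Two readings suffer: any side-by-side look at local and distant tissue, and the noninjected lesion's own change from screening, because some subjects would contribute a pre-redose sample and others a post-redose sample.

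**Working it through.** The plan states no figure here, so the check is arithmetic on the windows in nominal days. Day 0 is the Cycle 3 Day 1 MK-1454 injection.

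**Inputs.** Injected lesion: Day −3 to Day 0, before MK-1454 (6.1.3). Noninjected lesion: Day 0 to Day +3, with before or after dosing on Day 0 not stated (6.1.3). Cycle length: 21 days. Previous MK-1454 dose: Cycle 2 Day 1 in an every-3-weeks (Q3W) cohort, or Cycle 2 Day 15 in a cohort dosed that day (6.1.3 makes Day 8 and Day 15 dosing depend on the cohort).

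**Step 1, largest gap within a pair.** 3 days before + 3 days after = 6 days.

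**Step 2, time since the last MK-1454 dose when the noninjected biopsy is postdose.**

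| Cohort | Injected lesion | Noninjected lesion | Difference |
|---|---|---|---|
| Q3W | 21 − 3 = 18 to 21 days | 0 to 3 days | 18 − 3 = 15 to 21 days |
| Dosed on Cycle 2 Day 15 | 7 − 3 = 4 to 7 days | 0 to 3 days | 4 − 3 = 1 to 7 days |

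**Step 3, what falls between the samples.** If the injected lesion is sampled on an earlier day, or on Day 0 before the infusion, both drugs come between it and a postdose noninjected biopsy. The injected-lesion text is anchored to MK-1454 only, so a same-day sample could be taken in the 0.5 to 4 hours after pembrolizumab. In that case only the MK-1454 injection comes between.

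**Step 4, the other schedules.**

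| Schedule | Injected lesion | Noninjected lesion | MK-1454 dose allowed between? |
|---|---|---|---|
| Arms 1 and 2, Cycle 3 Day 15 | 3 to 7 h after (5 ± 2) | same day to +3 days | No; the next dose is 7 days later |
| Part II, Cycle 2 Day 1 (Cycle 3 Day 1 optional) | −5 days to predose | up to 5 days before | No; in Cohorts A and B the previous dose is 7 days earlier |
| Arm 3, Cycle 3 Day 1 | −3 days to predose | same day to +3 days | Yes |

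The Arms 1 and 2 row takes a same-day noninjected biopsy as following the injection; that text does not state the order either.

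**Step 5, can analysis repair it?** Not within a split pair. The injected lesion has no postdose sample at that visit, so lesion type and time since dose cannot be separated.

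**Step 6, cytokines.** The within-visit change at Cycle 5 Day 1 is the 4 h or 6 h value minus the same-day predose value. Arm 3 schedules no such predose value, so this change cannot be formed. The change from the Cycle 1 Day 1 predose value can.

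**The case against.** The strongest reply is that no planned analysis contrasts injected with noninjected tissue. Exploratory objective 6b in Section 3.3 compares tissue before and after treatment, and the objective on noninjected lesions is measured by imaging under itRECIST. The split is also only permitted: same day is preferred, and a same-day predose noninjected biopsy complies. Both points stand and limit the size of the problem. They do not remove it, because the noninjected lesion's before/after change still mixes timings.

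A reader might infer that every Arm 3 pair is confounded. The text does not support that: it affects only subjects who reach the visit, have an available noninjected site that can be biopsied safely, and use the later window.

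A reader might also infer that the distant effect will look too large. The documents give no time course for noninjected tissue after a dose, and the 4 h and 6 h samples are blood, so the direction is unknown.

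A third inference is that dose selection is at risk. Section 2.1.1 lets pharmacodynamic data inform the recommended Phase 2 dose, but no rule ties the Arm 3 choice to these biopsy pairs. Likewise, the TNF-α trigger applies to the first cycle of Arms 1 and 2 only, so the cytokine gap affects no Arm 3 escalation rule.

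Finally, aligning the windows will not make Arm 3 and Part II pairs interchangeable: Part II's main on-treatment biopsy is a cycle earlier, and its noninjected biopsy is not required.

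**Conclusion.** The inconsistency is real and worth correcting, but its reach is narrow. As written, Arm 3 allows a pair to straddle the Cycle 3 Day 1 (or optional Cycle 6 Day 1) dose, with samples up to 6 days apart. At Cycle 3 Day 1 the injected lesion is then about 18 to 21 days from its previous MK-1454 dose in Q3W cohorts, and less in cohorts dosed more often (about 4 to 7 days after a Cycle 2 Day 15 dose), against 0 to 3 days for the noninjected lesion.

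Only exploratory tissue work is touched. The primary safety, pharmacokinetic and response-rate analyses and the sample size do not depend on it. The planned Arm 3 enrolment of about 35 is an upper bound on the subjects affected; the documents give no basis for estimating how many would use the later window. The day counts assume nominal visits, ignore the ±3-day visit windows, and use only the dosing days that remain legible.

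The cytokine mismatch is secondary: it loses the within-visit Cycle 5 Day 1 change, not the change from the Cycle 1 Day 1 baseline.

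**What to change.** In Section 6.1.3, give both lesions one window at Cycle 3 Day 1 and Cycle 6 Day 1: *on the same day prior to pembrolizumab and MK-1454 administration, or up to 3 days prior to treatment*. The injected-lesion text must change too. Changing only the noninjected text could leave a pair split across the infusion, since the injected lesion is at present anchored to MK-1454 alone.

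For pairs already collected, use the actual biopsy-to-dose times for both drugs and analyse split pairs separately from pairs taken on one side of the dose.

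In the Arm 3 cytokine and CRP note, add the Cycle 5 Day 1 predose sample, as in Sections 6.1.2 and 6.2.1.

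The cost is small. No biopsy is added. The days after dosing are no longer available for scheduling the noninjected biopsy, but an equally long window before dosing replaces them. The cytokine change adds one serum tube at a visit where Arm 3 already draws biomarker blood before pembrolizumab.

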Tumor Imaging, RECIST, irRECIST, and/or itRECIST Response Assessment Cohort B	X									X	X	To be performed at 9 weeks (± 7 days) after the first dose, and then every 9 weeks thereafter. Tumor imaging (CT, PET/CT, or MRI, as indicated for tumor type), and medical photography should be performed on the same schedule, following calendar days , and should not be adjusted for
Medical Photography (Cutaneous Lesions)	X									X	X	delays in cycle starts. Continue imaging schedule until disease progression, discontinuation, or EOT. Medical photography can be performed more often as medically warranted.
	Safety Asse	essme	nts an	d Proc	edure	3						See Procedures Manual for Collection And Management of Samples.
AE Monitoring		(=									- →	
Full Physical Examination	X	X			X			X			X	
Directed Physical Examination			X	X		X	X					
Weight	X	X			X			X			X	
Height	X											
12-lead ECG	X											

Protocol/Amendment No.: 001-08

Trial Period	Screening		Treatment Phase MK-1454 Cycle = CCC then Q3W; or Q3W Pembrolizumab Cycle = 21 Days Cycle 4									
Cycle			Cvcle	1	(Cvcle 2	2	and		and	Notes	
Scheduling Day	-28 to -1	1	8	15	1	8	15	1	8	15	1	
Scheduled Window		±3	±3	±3	±3	±3	±3	±3	±3	±3	±3	
Vital Signs (temperature, pulse, respiratory rate, blood pressure, and oxygen (O ₂) saturation)	X	X	X	X	X	X	X	X	X	Х	X	Collect VS predose within 1 h (± 30 min) of MK-1454 administration at each treatment visit. Collect VS postdose on C1D1 at 2, 4, 6, and 8h (± 30 min for each time point) after MK-1454 administration. At each subsequent treatment visit, collect VS at 1 h (±15 min) after MK-1454 administration. Additional VS monitoring may be obtained as clinically indicated.
ECOG Performance Status	X	X			X			X			X	Additional ECOG can be performed as clinically indicated.
Tumor Markers	X	X			X			X			X	Specific tumor markers (eg, CEA, CA-125, CA-19-9, or alpha fetoprotein) to be obtained as clinically indicated.
CBC with Differential	X	X	X	X	X	X	X	X	X	X	X	Perform all screening clinical laboratory tests within 7 days
PT/INR and PTT or aPTT	X	X			X			X			X	prior to C1D1. Tests performed prior to the subject signing consent as part of routine clinical management are acceptable
Chemistry Panel	X	X	X	X	X	X	X	X	X	X	X	in lieu of a screening test, if the test is performed within the
LDH, GGT	X	X			X			X			X	specified time frame. For C1D1 and subsequent cycles
Urinalysis	X	X			X			X			X	testing must be performed within 72 h prior to dosing when scheduled. Does not need to be repeated on C1D1 if
Lipase and Amylase	X	X			X			X			X	screening labs were done within 72 hours of C1D1.
Pregnancy Test for WOCBP – Urine or Serum hCG	X	X										Required within 24 h prior to first dose of study medication. Does not need to be repeated if screening test was done within 24 hours of C1D1. If a urine pregnancy test cannot be confirmed as negative, a serum pregnancy test is required. Pregnancy testing must be done as required by local regulation. Where local regulations require monthly pregnancy testing per CTFG guidelines, see Appendix 12.5.
Thyroid Function (TSH, T3, FT3, T4, FT4)	X	X						X			X	Required within 72 hours prior to Day 1 of C1, C3, C5, C7, C9, C11, and at every other subsequent treatment cycle. Does not need to be repeated on C1D1 if screening labs were done within 72 hours of C1D1.
HIV, Hepatitis B and C screen (per site SOP)	X											Include HCV antibody or HCV RNA (qualitative) and HBsAg.

MK-1454-001-08 Final Protocol 27-Jul-2021 Confidential

Protocol/Amendment No.: 001-08

Trial Period	Screening		Treatment Phase MK-1454 Cycle = COI then Q3W; or Q3W Pembrolizumab Cycle = 21 Days Cycle 4									
			~ .		_				~		and	
Cycle	20.4 4		Cycle		1	Cycle 2		_	Cyc		Beyond	Notes
Scheduling Day Scheduled Window	-28 to -1	1	8	15	1	8	15	1	8	15	1	
Scheduled Window	Lab	_	±3 ±3 ±3 ±3 ±3 ±3 ±3 ±3								See Procedures Manual for Collection and Management of Samples.	
Serum for Cytokine Panel and CRP for MK-1454 Pharmacodynamics ^b	X	X			X						X·	Cytokine and CRP samples should be obtained at Screening, and predose on C1D1, C2D1 and C5D1, either both in the morning (8 AM to 12 PM) or both in the afternoon (1 PM to 5 PM). Postdose serum samples for cytokine panels and CRP will be collected on C1D1, C2D1, and C5D1. Postdose samples will be collected at 4 h (±15 min) and 6 h (±15 min) after MK-1454 administration. Collect samples at the same time as for MK-1454 PK when feasible.
Plasma MK-1454 PK ^b		X			X						X	Collect predose samples 1-8 h before MK-1454 administration on C1D1 and C2D1. Collect postdose samples on C1D1 and C2D1 at the following time points: end of IT injection (up to +15 min), 0.5 h (±15 min), 1 h (±15 min), 1.5 h (±15 min), 4 h (±15 min), and 6 h (±15 min). Collect samples at the same time as for cytokines and CRP, and for pembrolizumab PK, when feasible.

Protocol/Amendment No.: 001-08

Trial Period	Screening			MK-1	454 C Pem	ycle =	CCI	ent Ph th Cyclo		W; or Q3V Days		
Cycle	Screening		Cycle	1	(Cycle 2	2		Cycle 4 and Beyond		and	Notes
Scheduling Day	-28 to -1	1	8	15	1	8	15	1	8	15	1	
Scheduled Window		±3	±3	±3	±3	±3	±3	±3	±3	±3	±3	
Serum for Pembrolizumab PK		X			X						X	Collect samples predose 0 to 4 h before pembrolizumab IV infusion on C1D1, C2D1, C4D1, and on Day 1 of every 4
Serum for ADA		X			X						X	cycles thereafter (ie, C8, C12, etc.). Collect pembrolizumab and MK-1454 PK samples together, when feasible.
Blood for Plasma Biomarker Analysis					X						X	Collect prior to MK-1454 administration (Arm 1) and prior to pembrolizumab administration (Arm 2) on C2D1 and C5D1.
Blood for Serum Biomarker Analysis					X						X	
Blood for RNA Analysis		X										Collect predose 0-4 h before MK-1454 administration on C1D1 Collect postdose 6 h (±15 min) after MK-1454 administration on C1D1.
Blood for Genetic Analysis ^c		X										Collect prior to treatment.
Tumor Tissue Biopsy ^d	Х				X			X				For the tumor lesion that is treated with IT administration of MK-1454, collect predose tumor biopsy on the same day as treatment prior to IT administration of MK-1454, or up to 5 days prior to treatment on C2D1 and on C3D1 (optional). If available, biopsy of a distant, discrete, noninjected site may be performed up to 5 days before treatment of the injected lesion.

AE = adverse event; aPTT = activated partial thromboplastin time; CBC = complete blood count; CRP = C-reactive protein; CT = computed tomography; CTCL = cutaneous Tcell lymphoma; ECOG = Eastern Cooperative Oncology Group; EOT = end of treatment; FBR = future biomedical research; (F)T3 = (free) triiodothyronine; (F)T4 = (free) thyroxine; GGT = gamma glutamyl transferase; hCG = human chorionic gonadotropin; HCV = hepatitis C virus; HIV = human immunodeficiency virus; HNSCC = Head and Neck Squamous Cell Carcinoma; HPV = human papillomavirus; INR = international normalized ratio; irRECIST = immune-related RECIST; ISCL = International Society for Cutaneous Lymphomas; IT = intratumoral; LDH = lactate dehydrogenase; MRI = magnetic resonance imaging; NASBA = nucleic acid sequence-based amplification; PET = positron emission tomography; PK = pharmacokinetics; PT = prothrombin time; PTT = partial thromboplastin time; RECIST v1.1 = Response Evaluation Criteria In Solid Tumors, version 1.1; RNA = ribonucleic acid; TSH = thyroid-stimulating hormone; WOCBP = women of childbearing potential.

087V73

Protocol/Amendment No.: 001-08

Trial Period	Screening			MK-1		ycle =	CCI			W; or Q3V Days	V	
	Screening										Cycle 4	
											and	
Cycle			Cycle	1	C	ycle 2	2		Cycl	e 3	Beyond	Notes
Scheduling Day	-28 to -1	1	8	15	1	8	15	1	8	15	1	
Scheduled Window		±3	±3	±3	±3	±3	±3	±3	±3	±3	±3	

a) The observation period may be extended at the discretion of the investigator, per local IRB/IEC, and/or Health Authority mandate.

- b) Up to 2 additional serum samples may be collected if deemed medically necessary (eg. in the setting of an AE).
- c) This sample will be drawn for genetic variations in ADME and planned analysis of the association between genetic variants in DNA and drug response. If the IRB/IEC does not approve of the planned analysis of the association between DNA variation and drug response, or if there is a local law or regulation prohibiting the same, then data analysis will be limited to investigate ADME genetic variations. If the sample is collected, leftover extracted DNA will be stored for FBR if the participant (or their legally acceptable representative) provides documented informed consent for FBR. If the planned genetic analysis is not approved, but FBR is approved and consent is given, then this sample will be collected for the purpose of FBR.
- d) All subjects will be required to provide a sample biopsy of the tumor to be injected with MK-1454 and, if available, a sample biopsy from a distant, discrete noninjected site (at least 2 biopsies at each site), unless deemed medically unsafe by the investigator. For the tumor lesion intended for treatment with IT administration of MK-1454, the sample will be obtained by either punch biopsy for cutaneous lesions, or ultrasound guided biopsy for subcutaneous lesions. If available, for distant, discrete tumor lesions that are not intended for IT administration with MK-1454, the sample biopsy will be obtained by punch biopsy for cutaneous lesions, ultrasound guided biopsy for subcutaneous/visceral lesions, or image-guided biopsy, such as CT-guided biopsy, for visceral and deeper tumor lesions. Method of biopsy will be per guidance of the investigator as well as discussion with the Sponsor. Instructions for tissue collection, processing, and shipment are provided in the Procedures Manual. Leftover main study tissue will be stored for FBR if the subject consents to FBR. Instructions for tissue collection, processing, and shipment are provided in the Procedures Manual.

Protocol/Amendment No.: 001-08

6.2.2 Discontinuation / End of Treatment and Posttreatment Follow-up for Part II – Expansion Cohorts

		Posttreatme	ent Period	
Trial Period	End of Treatment (EOT)/ Discontinuation	30-Day Safety Follow-up Visit	Survival Follow-up	Notes
Scheduling Day		30 days post last dose	Q12W	
Scheduled Window	±7	+7	±14	
Administrative Procedures				
Prior Medication and Concomitant Medication Review	X	X		
Efficacy Procedures				
Tumor Imaging, RECIST, irRECIST, and/or itRECIST Response Assessment	X			
Medical Photography (Cutaneous Lesions)	X			
Survival Status Monitoring	<			Updated survival status may be requested by the Sponsor at any time during the course of the study. Upon Sponsor notification, all subjects who do not/will not have a scheduled study visit or study contact during the Sponsor defined time period will be contacted for their survival status (excluding subjects that have a death event previously recorded). See Procedures Manual for collection
Safety Assessments and Procedures				and management of samples.
AE Monitoring	X	X		
Full Physical Examination	X	X		
Weight	X	X		
12-lead ECG	X			
Vital Signs	X	X		Temperature, pulse, respiratory rate, blood pressure, and O ₂ saturation
ECOG Performance Status	X	X		
CBC with Differential	X	X		
Chemistry Panel	X	X		
Lipase and Amylase	X	X		
Pregnancy Test for WOCBP – Urine or Serum hCG		X		For WOCBP, perform as required locally. If a urine pregnancy test cannot be confirmed as negative, a serum pregnancy test is required.

MK-1454-001-08 Final Protocol 27-Jul-2021 Confidential

Protocol/Amendment No.: 001-08

		Posttreatm	ent Period	
	End of Treatment (EOT)/	30-Day Safety	Survival	
Trial Period	Discontinuation	Follow-up Visit	Follow-up	Notes
Scheduling Day		30 days post last dose	Q12W	
Scheduled Window	±7	+7	±14	
Thyroid Function (TSH, T3, FT3, T4, FT4)		X		
Pharmacokinetics (PK)/Pharmacodynamics/ Future	Biomedical Research/Biomark	ers		See Procedures Manual for collection and management of samples.
Serum for Pembrolizumab PK	X			Only for pembrolizumab-treated
Serum for ADA	X			subjects.
Blood for Plasma Biomarker Analysis	X			
Blood for Serum Biomarker Analysis	X			

ADA = antidrug antibodies; AE = adverse event; CT = computed tomography; DNA = deoxyribonucleic acid; ECG = electrocardiogram; ECOG = Eastern Cooperative Oncology Group; (F)T3 = (free) triiodothyronine; (F)T4 = (free) thyroxine; hCG = human chorionic gonadotropin; irRECIST = immune-related RECIST; MRI = magnetic resonance imaging; PET = positron emission tomography; RECIST v1.1 = Response Evaluation Criteria In Solid Tumors, version 1.1; RNA = ribonucleic acid; TSH = thyroidstimulating hormone; WOCBP = women of childbearing potential.

Protocol/Amendment No.: 001-08

